## 7.2. Adverse Event Collection & Reporting

### Anticipated events

Given that many people who are HIV+ and smokers have more medical needs than the general population, we do anticipate subjects will report a higher rate of Adverse Events (AEs) as an inherent characteristic of this population. These include such events as COPD, lung cancer, pneumonia, psychiatric symptoms, and Antiretroviral Therapy medication side effects.

Some anticipated AEs resulting from the study interventions include study drug side effects. The study drug (i.e. NRT) has some common side effects that we expect subjects to occasionally report, including: dizziness, headaches, rapid heart rate, increased blood pressure, nausea and diarrhea. For the nicotine patch in particular, common side effects include skin irritation and/or itching where the patch is placed, insomnia, and vivid dreaming.

In addition, quitting smoking can result in withdrawal symptoms that may be uncomfortable to the participant. Common withdrawal symptoms include: cravings for cigarettes; depressed or sad mood; insomnia or trouble sleeping; feeling irritable, on edge, or grouchy; trouble concentrating; restlessness; decreased heart rate; and increased appetite/weight gain.

There may be some risks associated with smartphone and app usage. Events that we anticipate subjects may report to us around using the study smartphone include sleep disturbances (from high frequency use), eye strain (from viewing the screen), and data breaches (if subjects enter their personal information in the phone).

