### Collecting and recording AEs

We will be tracking all AEs and serious adverse events (SAEs) that a participant may experience once starting the study intervention (from Baseline onward). We will be doing this throughout the study, regardless of whether or not we think they are related to the study intervention. AEs will be documented by research personnel during research assessments, or at any other time during the clinical trial that they have contact with or about the subject. The PIs and study doctor are responsible for oversight on AEs.

We will document each AE with details such as:

- Description of event;
- Start and stop dates (if applicable);
- Whether or not they are getting treated (e.g. medications or therapies);
- Whether or not it is considered an SAE;
- Any other pertinent details.

Collected AEs will be documented and recorded with the information above on AE forms and entered into an electronic database (i.e., REDCap). On a weekly basis, the PI will review each AE to determine the following:

- Relationship to the study intervention;
- Severity of the event;
- Outcome;
- Status: ongoing, closed, lost to follow-up;
- Deciding what course of action should be taken to address the AE.

The PI may consult with the study physician if needed.

If the participant reports a SAE, the same collection and recording procedures will take place as with AEs. However, research staff will alert the PI to the SAE as soon as possible (within 24 hours of a reported SAE). The PI will review the reported SAE within 24 hours of becoming aware of it. SAEs will have a separate form completed for each one that's reported.

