## 8.0. Data Analysis and Sample Size

### 8.1. Determination of Sample Size

Given that this is primarily a feasibility and acceptability trial, we expect the intervention effect sizes to have notable variance (i.e., wide confidence intervals), thus the relevance of the current study is linked to its significance and potential impact to the field, and not on its ability to estimate parameter estimates in the population. In this scenario, a precision (rather than power) approach is especially suited, since calculating confidence intervals is ideal for preliminary or pilot investigations, and facilitates that sample size is determined by practical rather than formal considerations. Given that retention is a key issue in smoking cessation studies, we will focus on this primary outcome. A pilot study of LTQ and prior studies in the general population of ACT-based interventions for smoking cessation show 93% 6-month participant retention, and 70% for standard of care.

Further, with 30 participants per group, we calculated that we would have 70%, 75% and 80% power to detect abstinence rates of 0.32, 0.34, and 0.36 effect sizes, respectively.

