**Chi-square tests and logistic regression:**

- Quit attempts (prevalence of any quit attempts, yes/no)
- 7-day point prevalence abstinence (prevalence of any verified abstinence, yes/no)
- Adherence to NRT (prevalence of use of optimal amount of NRT, yes/no)
- Participant safety (prevalence of any adverse events, yes/no)

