**t-tests and linear regression:**

- Change in CPD (measured as a continuous variable)
- Quit attempts (total number of quit attempts, measured as a continuous variable)
- Adherence to NRT (overall % of NRT used as directed, measured as a continuous variable)
- Participant safety (total number of adverse events, measured as a continuous variable)

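### Section 8.2 compares safety between arms only on pooled all-cause adverse events, so more quitting with LTQ-H could appear as an excess of events with no app harm, and no breakdown is planned that would show it

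*Combined protocol and SAP*

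**What the plan says.** Section 8.2 lists participant safety among the secondary outcomes to be compared between LTQ-H and QuitGuide, and defines it in two ways. Under chi-square tests and logistic regression it is "Participant safety (prevalence of any adverse events, yes/no". Under t-tests and linear regression it is "Participant safety (total number of adverse events, measured as a continuous variable". No other between-arm safety analysis is planned.

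Section 7.2 (Collecting and recording AEs) tracks every AE and SAE from baseline, "regardless of whether or not we think they are related to the study intervention". It has the PI review each AE weekly for relatedness and severity, among other things, and records whether it is serious. Section 8.2 uses none of these fields.

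Section 7.2 (Anticipated events) sets four kinds of event side by side:
- background illness: "we do anticipate subjects will report a higher rate of Adverse Events (AEs) as an inherent characteristic of this population"
- side effects of the patch
- withdrawal: "quitting smoking can result in withdrawal symptoms that may be uncomfortable to the participant", with a list that includes cravings, low mood, insomnia and irritability
- smartphone and app events, such as eye strain

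Nothing excludes withdrawal symptoms from the AE count or has them reported separately.

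**The concern.** Withdrawal symptoms partly follow from the benefit that the trial hopes to show. Randomisation makes the arms alike at baseline, but it does not equalise events that arise later because one app leads more people to quit. If LTQ-H works better, its all-cause AE total can rise for that reason alone, and a reader of the planned output could not tell this from app harm.

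Background illness acts differently. It is the same in both arms in expectation, so it adds noise and makes a true between-arm difference in app or patch events harder to see.

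Section 4.1 schedules an R01 application after this pilot. The safety result would be carried into it without the information needed to interpret it.

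**Working it through.** **The plan's own figures.** Section 8.1 gives no power or rates for safety. Its only power statement concerns abstinence: "with 30 participants per group, we calculated that we would have 70%, 75% and 80% power" at effect sizes 0.32, 0.34 and 0.36. Read as Cohen's w with N = 60 and two-sided alpha 0.05 (not stated, assumed), the noncentrality is N × w² = 6.14, 6.94 and 7.78. Power is then 69.8%, 75.0% and 79.6%, which matches. This says nothing about the safety tests. It is used below only to choose a large quitting difference: 30% v 64% gives w = 0.341 and 12% v 42% gives w = 0.338, while 10% v 44% gives w = 0.383, somewhat above the plan's range.

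**Inputs for the safety comparison.** From the documents: 30 per arm, 1:1 allocation, AEs of all causes. Assumed, because no rates are given:
- background AEs negative binomial with mean m = 1 or 2 per person and shape 1.5, the same in both arms
- a share q of each arm has withdrawal, with a Poisson number of reported symptoms, mean s = 1 to 3
- no harm from either app; two-sided 5%

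**Formulas.** Expected excess in LTQ-H = (q₁ − q₀) × s. Variance in an arm = m + m²/1.5 + q·s + q(1 − q)·s².

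**Hand check, high end** (10% v 44%, s = 3, m = 1). Excess = 0.34 × 3 = 1.02 AEs per person. Variances are 2.78 and 5.20, so the standard error is √((2.78 + 5.20)/30) = 0.516. The ratio is 1.98, and the rejection probability is about Φ(1.98 − 1.96) = 51%.

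**Hand check, low end** (70% v 80%, s = 3, m = 1). Excess = 0.10 × 3 = 0.30. Variances are 5.66 and 5.51, the standard error is 0.610 and the ratio is 0.49. The two tails give about 7.1% + 0.7% = 7.8%.

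**Simulation, 20,000 trials per setting, over all m and s:**

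| Who has withdrawal (QuitGuide v LTQ-H) | t-test, total AEs | chi-square, any AE |
|---|---|---|
| Equal, 50% v 50% | about 5% | about 5% |
| Attempters, 70% v 80% or 80% v 90% | 5-8% | 5-9% |
| Quitters only, 12% v 42% | 8-41% | 7-19% |
| Quitters only, 30% v 64% | 9-42% | 8-26% |
| Quitters only, 10% v 44% | 9-51% | 8-23% |

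In the quitters-only rows almost all rejections go against LTQ-H. A separate normal approximation for attempts of 40% v 60%, with slightly less background variance, gives 5-17%.

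**Dilution.** Suppose intervention-caused events occur in 5% v 30% of participants, independent of background (assumed). With background risk b, the any-AE risk is 1 − (1 − b)(1 − r). For b = 50% this is 52.5% v 65%.

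| Background risk b of the outcome compared | Chi-square power |
|---|---|
| 0% | 78% |
| 10% | 52% |
| 20% | 37% |
| 30% | 28% |
| 50% | 16% |
| 80% | 8% |
| 90% | 6% |

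At 5% v 15% with no background at all, power is only 26%.

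**The case against.** Five points can fairly be made against this.

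- **Everyone in the trial is trying to quit.** Section 3.1 requires interest in quitting, and section 6.3 has all participants start patches on a quit date within 4 weeks of baseline. Failed attempts also bring withdrawal, in both arms. If withdrawal tracks attempts, the excess is small. This stands, and it is why the low end of the range is close to 5%.
- **Rejection in these settings is not a false positive.** The arms then truly differ in AE burden, and the test rejects the null that it tests. This also stands. A reader might infer an inflated type I error; the fault lies in what the difference can be taken to mean.
- **Background illness is randomised.** A reader might infer that the tests mainly compare background illness, or that the yes/no outcome sits at its ceiling. The documents do not support either: no AE rate is given, and background events add noise without direction.
- **Both arms are supplied with patches on the same scheme (section 5.1).** Patch harm common to both arms is invisible to any between-arm comparison. Only a difference, for instance through different patch use, can be diluted.
- **All-cause comparison has merit.** It avoids subjective attribution and captures unanticipated harms. A reader might conclude that it should give way to a comparison limited to listed patch and app events. That would drop unanticipated harms, and the lists overlap with withdrawal and ordinary illness. With quitting at 10% v 44% or 30% v 64%, 30-50% of quitters reporting an overlapping symptom and 10-30% having another listed event (all assumed), such a test still rejects in about 9-29% of trials of equally safe apps.

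The consequence is also bounded. Safety is the last of five secondary outcomes, no decision rule uses these tests, and individual safety oversight runs separately under section 7.2.

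**Conclusion.** The point holds in a limited form. The only between-arm safety analyses pool all causes, include withdrawal symptoms that quitting itself can bring, and leave collected relatedness, severity and seriousness data unused. If LTQ-H increases quitting, the comparison can show an AE excess without app harm.

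The size cannot be derived from the documents. It runs from about 5-8% rejection on total AEs (attempts differing by 10 points) to at most about 40-50% (withdrawal in quitters only, quitting differing by 30-34 points, three symptoms each, one background AE per person). The upper figures need a gap as large as the effect sizes in section 8.1, which are power inputs and not forecasts. They also need staff to log withdrawal symptoms as AEs, which the protocol neither requires nor rules out. Dilution by background events is real, but its size is equally assumed.

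The all-cause comparison is not wrong in itself. What is missing is the breakdown that would let it be interpreted.

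**What to change.** Keep both all-cause analyses in section 8.2 and add the following by arm, with risk differences (differences in means for counts) and 95% confidence intervals:

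1. Participants with at least one AE, and the AE count, with the withdrawal symptoms listed in section 7.2 shown separately and the all-cause comparison repeated without them.
2. AEs by PI-rated relatedness and severity, by seriousness, and by type: patch, app, withdrawal, other.

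State that any all-cause difference will be interpreted alongside this breakdown. Withdrawal symptoms should not be declared harmless: low mood is on that list, and the trial monitors psychiatric symptoms and suicidality. Show terms that belong to two types, such as insomnia, under both, and say in advance how they are treated in the repeated comparison.

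The cost is SAP wording and coding of AE forms already in REDCap, with some judgement on overlapping terms. No new data or visits are needed. Intervals suit the precision approach of section 8.1 better than further tests at 30 per arm.

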## Appendix

### List of Abbreviations

ROI – Release of information

ICF – Informed consent form

Con meds – Concomitant medications

AE – Adverse event

SAE – Serious adverse event

CO – Carbon monoxide

BAL – Breath alcohol level

BP – Blood pressure

HR – Heart rate

NRT – Nicotine replacement therapy

LTQ-H – Learn to Quit-HIV

QG – QuitGuide

NCI – National Cancer institute

RA – Research assistant

CPD – Cigarettes-per-day

UE – User engagement

UX – User experience

CfAST – Center for Addiction Science and Technology

PLWH – Persons living with HIV

RCT – Randomized controlled trial

PPM – Parts per million

PII – Personally Identifiable Information
